2- The cardiologists will evaluate whether the quality of each clip is good enough for their interpretation (binary yes/no) (Yes : ACEP $\geq$  3)..

3- The cardiologists will determine on the ultrasound measurements: (qualitative yes/no)

- Is there a left ventricular hypertrophy?
- Is there a right ventricular hypertrophy?
- Is there a dilation of the left ventricle?
- Is there a dilation of the right ventricle?
- Is there a dilation of the left atrium?
- Is there a dilation of the right atrium?
- Is there an abnormal left ventricular function?
- Is there an abnormal right ventricular function?
- Is there an abnormal mitral valve?
- Is there an abnormal tricuspid valve?
- Is there an abnormal aortic valve?
- Is there a pericardial effusion?
- Is there a dilatation of the inferior vena cava?
- Is there a kinetic disorder?
- Is there another abnormality? (comments)

4- The cardiologists will determine on the acquisitions the following ultrasound measurements (quantitative)

- Left ventricular
  - End-systolic and end-diastolic volumes
  - Left ventricular function.
  - Left ventricular parameters will be assessed by cardiologists using the Simpson Biplane method and through the HeartEF algorithm developed by DESKi.
- Parasternal analysis
  - Septal wall thickness
  - Posterior wall thickness
  - Internal diameter of the left ventricle (systole and diastole)

DESKI	PROSPECTIVE EVALUATION OF HEARTFOCUS: A SOFTWARE SUPPORTING THE ACQUISITION OF CARDIAC ULTRASOUND EXAMS	HF-01 Version:4.2
-------	---------------------------------------------------------------------------------------------------------	----------------------

	
 
○ Aortic diameter
 
● Diameter of the inferior vena cava
 
 
5- The acquisition time for the limited ultrasound exam

MEDICAL DEVICES / CLINICAL INVESTIGATION STRATEGIES /PROCEDURES	
The HeartFocus software has not yet obtained the FDA or CE certification. This clinical trial aims to collect clinical evidence for FDA and CE certification.
 
The device is classified as Class IIa - software under MDR in Europe and Class II in US following FDA classification.
 
HeartFocus software is compatible with the ultrasound probe Clarius phased array. This probe has received FDA certification and CE certification.

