ANALYSIS	
Patient description: The population will be described in terms of demographics, ultrasound parameters, and pathology.
 
Endpoints: For all quality criteria, the percentage of success and its confidence interval will be evaluated for acquisitions performed by experts and acquisitions performed by novices. This analysis will be performed via a multi-reader, multi-case power analysis.
 
For each qualitative ultrasound measurement, taking into account the experts' acquisition as the reference, the following parameters will be evaluated:
 
 
● Percentage of agreement
 
● Sensitivity
 
● Specificity
 
● Precision
 
● Recall
 
● F1-score
 
● Area under the curve
 
 
For each quantitative ultrasound measurement:
 
 
● The mean, standard deviation and 95% confidence interval of the difference will be calculated between the measurements made on the acquisitions obtained by the experts and those obtained by the novices
 
● Bland-Altman plots and correlation plots will be performed.
 
 
Sensitivity studies will be performed on the investigating centers, prior cardiac diagnoses, and obese patients.

DESKi	PROSPECTIVE EVALUATION OF HEARTFOCUS: A SOFTWARE SUPPORTING THE ACQUISITION OF CARDIAC ULTRASOUND EXAMS	HF-01 Version:4.2
-------	---------------------------------------------------------------------------------------------------------	----------------------

	The evaluation of HeartEF will be performed by comparing the results from the algorithm to the manual cardiologist's analysis.
--	--------------------------------------------------------------------------------------------------------------------------------

EXPECTED IMPACTS	
From a medical point of view, there will be no direct benefit for the patient included in the analysis.
 
At a larger scale, HeartFocus software will outlook access to ultrasound exams by allowing non-experts (emergency physicians, residents, general practitioners, paramedics, and nurses) to acquire cardiac ultrasound exams of sufficient quality for their analysis, without any previous experience in echography.
 
This would improve patient management by optimizing the care pathway, with echography being used as a screening or follow-up tool for patients.

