3.4.2 Clinical Endpoints

3.4.2.1 Qualitative Endpoints

Indicate the evaluation when the entire exam allows the qualitative visual assessment of

- left ventricular size (normal or borderline, hypertrophy, dilation, hypertrophy and dilation),
- global left ventricular function (normal or borderline, reduced (EF ≤ 50 %)),
- right ventricular size (normal or borderline, hypertrophy, dilation, hypertrophy and dilation),
- non-trivial pericardial effusion (absent, present),
- right ventricular function (normal or borderline, reduced),
- left atrial size (normal or borderline, abnormal (enlarged)),
- right atrial size (normal or borderline, abnormal (enlarged)),
- segmental kinetics of the left ventricle (normal or borderline, abnormal),
- mitral valve (structurally normal, structurally abnormal, suspected device),
- tricuspid valve (structurally normal, structurally abnormal, suspected device),
- aortic valve (structurally normal, structurally abnormal, suspected device),
- inferior vena cava size (normal, dilated),

Any other abnormalities (free text) that can be visually assessed will be described in listings.

NB: For visual assessment of left ventricular size and right ventricular size, the choices "hypertrophy," "dilation," and "hypertrophy and dilation" can be grouped in a more general category: "abnormal (enlarged)."

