5.4.2.2 Clinical Qualitative Endpoints Analysis

For clinical qualitative endpoints, at least 3 of 5 cardiologists had to answer the endpoint. The value chosen by most cardiologists who answer the endpoint on the experts’ exam will be considered as the reference value. Similarly, the value chosen by most cardiologists who answer the endpoint on the novices’ exam will be considered as the tested value. For both exams, it is possible not to have a majority assessment among cardiologists, as only 4 cardiologists may answer the question.

For each clinical qualitative endpoint, the number of patients for whom both the reference and tested values are the same and are different will be computed. These figures will be presented in a confusion matrix similar to Table 1 (the categories will change according to the endpoint, see categories according to the endpoint in section 3.4.2.1). The percentage of the overall agreement will be calculated for each qualitative endpoint as the corresponding confidence interval.

		Experts' exams				% Overall Agreement and C.I.
		Normal or borderline	Reduced	No majority assessment among cardiologists	Total	
Novices' exams	Normal or borderline					-
	Reduced					-
	No majority assessment among cardiologists					-
	Total					

Table 1: Confusion matrix to compare novices' exams to experts' exams for the endpoint “qualitative visual assessment of right ventricular function”.

It is expected that not many exams will be counted in the “No majority assessment among cardiologists” category, either novice or expert exams. If this is not the case, a sensitive analysis will be conducted.

For each endpoint, the endpoint will be converted into a binary issue, answering the question “Is the structure normal?”, according to the following rules:

- “yes” if the answer to the endpoint is:
 - “normal or borderline” or “structurally normal” or “normal”
 - “absent”
- “no” if the answer to the endpoint is:
 - “hypertrophy”
 - “dilation”
 - “hypertrophy and dilation”
 - “reduced (EF ≤ 50 %)” or “reduced”
 - “present”
 - “abnormal” or “structurally abnormal” or “abnormal (enlarged)”
 - “suspected device”
 - “dilated”

Then, for each endpoint, and on the exams where there is a majority assessment among cardiologists, the following figures will be computed:

- Number of true positives (TP) when both the reference and tested values are positive,
- Number of false positives (FP) when the reference value is negative and the tested value is positive,

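### The SAP's accuracy metrics pool ventricular hypertrophy and dilation, which the protocol lists as separate endpoints, so a swap between the two scores as concordant and no type-specific metric is planned

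*SAP*

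**What the plan says.** **Protocol, Endpoints, secondary endpoint 3.** Each ventricle gets two yes/no questions. For the left they are "Is there a left ventricular hypertrophy" and "Is there a dilation of the left ventricle"; for the right, "Is there a right ventricular hypertrophy" and "Is there a dilation of the right ventricle".

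**Protocol, Analysis.** "For each qualitative ultrasound measurement, taking into account the experts' acquisition as the reference, the following parameters will be evaluated": the list includes percentage agreement, sensitivity, specificity, precision, recall and F1.

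**SAP 3.4.2.1.** Each pair of questions becomes one size item with four categories: normal or borderline, hypertrophy, dilation, or both. A note adds that the three abnormal categories "can be grouped in a more general category", labelled abnormal (enlarged).

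**SAP 5.4.2.2.** The value chosen by most responding cardiologists is taken for each exam, with the expert exam as reference. A confusion matrix on the 3.4.2.1 categories and an overall agreement with its confidence interval follow. Then "For each endpoint, the endpoint will be converted into a binary issue, answering the question" of whether the structure is normal. All three abnormal ventricular categories convert to *no*. True and false positives and negatives, accuracy, sensitivity, specificity, precision and F1 are computed from that binary answer, on exams with a majority assessment. Positive is not tied to either answer.

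The SAP introduction says the plan is based on protocol version 4.2. It does not mention or justify this change.

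**The concern.** Wall thickening and cavity enlargement are different findings, and the protocol treats them as different endpoints. If the expert exam shows dilation and the novice exam shows hypertrophy, the pair is wrong on both protocol questions: dilation is missed and hypertrophy is falsely reported. After the SAP's conversion the same pair is an agreement.

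At stake is a secondary objective, the agreement between novice and expert exams on echocardiographic parameters. As planned, the report would carry a sensitivity and an F1 for an abnormal ventricle, but none for the four abnormalities that the protocol names. A reader who has the protocol could take the pooled figure for the type-specific one.

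**Working it through.** The documents give no prevalence, swap rate or target for this endpoint, so there is no figure of the plan's to reproduce. The check has three parts.

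**1. How one swap is scored (SAP 5.4.2.2 rules).** Reference dilation becomes *no*; tested hypertrophy becomes *no*.
- If positive means abnormal, the pair is a true positive. It counts as correct in accuracy, sensitivity, precision and F1.
- If positive means *yes, normal* (the literal reading of the SAP's question), it is a true negative. It counts as correct in accuracy and specificity, and does not enter sensitivity, precision or F1.
- Accuracy is affected on both readings.

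**2. Size, on assumed counts.** Of 240 patients, the expert reference is 180 normal, 30 hypertrophy and 30 dilation, with none in the combined category. On the novice exam 10 normals are read as abnormal (5 of each type), 3 of each abnormal type are read as normal, and x patients are swapped in each direction.

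Pooled, positive = abnormal: TP = 54, FP = 10, FN = 6, TN = 170 for every x.
- Accuracy = (54 + 170)/240 = 0.933
- Sensitivity = 54/60 = 0.900
- F1 = 2×54/(2×54 + 10 + 6) = 108/124 = 0.871

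Pooled, positive = normal: accuracy 0.933, sensitivity 170/180 = 0.944, specificity 54/60 = 0.900, F1 = 340/356 = 0.955, again for every x.

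Dilation scored on its own (hypertrophy is identical by symmetry): TP = 27 − x, FN = 3 + x, FP = 5 + x, TN = 205 − x. Hence sensitivity = (27 − x)/30, F1 = (54 − 2x)/62 and accuracy = (232 − 2x)/240. Overall agreement in the unpooled matrix = (224 − 2x)/240.

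| x | Pooled accuracy | Dilation sensitivity | Dilation F1 | Dilation accuracy | Overall agreement |
|---|---|---|---|---|---|
| 0 | 0.933 | 0.90 | 0.871 | 0.967 | 0.933 |
| 3 | 0.933 | 0.80 | 0.774 | 0.942 | 0.908 |
| 6 | 0.933 | 0.70 | 0.677 | 0.917 | 0.883 |
| 12 | 0.933 | 0.50 | 0.484 | 0.867 | 0.833 |
| 27 | 0.933 | 0.00 | 0.000 | 0.742 | 0.708 |

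**3. Majority taken before conversion.** Suppose the five readers answer: 2 hypertrophy, 2 hypertrophy and dilation, 1 normal. No category leads, so the exam drops out of the binary metrics. Derived per reader, hypertrophy is present for 4 of 5 and dilation for 2 of 5, so both questions have a clear majority answer.

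Now suppose 2 answer normal and 1 each gives hypertrophy, dilation and both. Normal has the most votes, although 3 of 5 call the ventricle abnormal. The exam becomes normal if the SAP means the most frequent value, or drops out if it means more than half. The SAP mentions only the case of four responders as a reason for having no majority.

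**The case against.** The strongest reply is that the type information is not lost. The confusion matrix keeps all four categories, and overall agreement falls with each swap, as the last column of the table shows. SAP 3.4.2.2 and 5.4.2.3 also compare septal and posterior wall thickness, left ventricular diameters and left ventricular volumes between novice and expert exams, so wall and cavity are examined separately for the left ventricle. The grouping in 3.4.2.1 is optional. All this stands. A reader might infer that the trial cannot report how novice exams show dilation or hypertrophy; the documents do not support that. What is missing is the planned type-specific metrics. The matrix replaces them only in part, because exams split across abnormal types can lose their majority, and the right ventricle has no quantitative counterpart.

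A reader might also infer that the pooled metrics are biased upward. That does not hold in general. They answer a different, stated question, and with no swaps pooled accuracy (0.933) lies below dilation accuracy (0.967). Sensitivity can differ in either direction too. Assume 45 hypertrophies, of which 42 are read as such and 3 as normal, and 15 dilations, of which 8 are read as such, 5 as hypertrophy and 2 as normal. With positive = abnormal, pooled sensitivity is (42 + 13)/60 = 91.7%, between 42/45 = 93.3% for hypertrophy and 8/15 = 53.3% for dilation.

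Nor can one say without condition that sensitivity and F1 are affected, since positive is undefined. Finally, it is tempting to extend the point to valves, where a suspected device and a structural abnormality are pooled. The protocol asks a single abnormal-or-not question per valve, so that pooling is compatible with it.

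**Conclusion.** The point holds as a departure from the protocol's secondary endpoint 3. Four endpoints with promised metrics are reduced to two pooled ones without a stated reason, and a dilation/hypertrophy swap is scored as concordant in every pooled metric that it enters. That always includes accuracy; the other metrics depend on a definition that the SAP leaves open.

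The size cannot be derived from the documents. It depends on how often the panel's value swaps type between the two exams, and on the mix of abnormalities. The figures above are illustrations on assumed counts; if swaps are rare, the practical effect is small. The endpoints are descriptive, with no threshold or test attached, and the success criterion in SAP 3.3 rests only on whether structures can be assessed, so it is unaffected. The change should be made because it restores a protocol commitment at little cost.

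**What to change.** In SAP 5.4.2.2:

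1. Define positive as abnormality present, in line with the protocol's question form.
2. For each cardiologist and each ventricle, derive two yes/no answers from the category already recorded: hypertrophy (yes if *hypertrophy* or *hypertrophy and dilation*) and dilation (yes if *dilation* or *hypertrophy and dilation*).
3. Take the panel majority on each derived answer, then report TP, FP, FN, TN and the metrics for the four endpoints. With five responders a yes/no answer always has a majority; with four, a 2–2 tie remains possible and stays in the no-majority category.
4. Keep the pooled result as an extra row, labelled abnormal rather than abnormal (enlarged), and keep the four-category matrix ungrouped.

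If the sponsor prefers pooling alone, the SAP should state and justify the departure from the protocol.

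The cost is SAP wording and a few output rows, with no new data. The downside is fewer positives per endpoint and so wider uncertainty. In the first illustration, at a sensitivity of 0.90, the simple binomial standard error rises from √(0.9×0.1/60) = 0.039 with 60 positives to √(0.9×0.1/30) = 0.055 with 30.

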- Number of false negatives (FN) when the reference value is positive and the tested value is negative,
- Number of true negatives (TN) when both the reference and tested values are negative.

In addition, based on these figures, the following metrics will be computed:

- Accuracy, calculated using the formula: $(TP + TN) / (TP + FP + FN + TN)$,
- Sensitivity (= recall), calculated using the formula: $TP / (TP + FN)$,
- Specificity, calculated using the formula: $TN / (TN + FP)$,
- Precision, calculated using the formula: $TP / (TP + FP)$,
- F1-score, calculated using the formula: $2 \times (\text{precision} \times \text{recall}) / (\text{precision} + \text{recall})$.

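### SAP 5.4.2.2 does not say which class is 'positive', and it votes before pooling categories, so sensitivity may describe normal structures and some majority-abnormal exams leave the metrics

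*SAP*

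**What the plan says.** SAP 5.4.2.2 works in this order:

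1. At least 3 of the 5 cardiologists must answer. "The value chosen by most cardiologists who answer the endpoint on the" experts' exam becomes the reference value, and the same rule applied to the novices' exam gives the tested value.
2. A vote may fail: "it is possible not to have a majority assessment among cardiologists, as only 4 cardiologists may answer the question". Such exams have their own row and column in the confusion matrix. Few are expected; "If this is not the case, a sensitive analysis will be conducted".
3. Next, "the endpoint will be converted into a binary issue, answering the question “Is the structure normal"? Normal or absent maps to yes. Every abnormal category, including suspected device, maps to no.
4. The counts are made "on the exams where there is a majority assessment among cardiologists". They are worded as "Number of true positives (TP) when both the reference and tested values are positive" and "Number of false negatives (FN) when the reference value is positive and the tested value is negative". Accuracy, sensitivity, specificity, precision and F1 follow from them.

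SAP 3.4.2.1 gives left and right ventricular size four categories each (one normal, three abnormal) and each of the mitral, tricuspid and aortic valves three (one normal, two mapped to no). The other seven of the 12 endpoints have two. A note there allows the abnormal size categories to be grouped.

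The protocol's secondary endpoint 3 is phrased the other way round, for example "Is there a left ventricular hypertrophy"? There, a yes means that an abnormality is present.

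**The concern.** Two things are left open, and both bear on how well novice exams reveal abnormality relative to expert exams.

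**Positive class.** The SAP never links 'positive' to yes or to no. Since its binary question is whether the structure is normal, the natural reading is yes = positive, so normal is the positive class. Anyone who takes 'sensitivity' as detection of abnormality would then be reading the rate at which normal structures are recognised. A missed abnormality is a key risk of a novice-acquired exam, and F1 would look high whenever abnormality is uncommon.

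**Order of voting and pooling.** The reference and tested values are fixed as the voted category before conversion to normal/abnormal. Normal is a single category, so a majority for normal can never be split. A majority for abnormal can be, because the votes spread over two or three types. Any loss of majority exams therefore falls only on exams that most readers called abnormal. The SAP's explanation, that a majority fails because four readers answered, is complete for two-category endpoints but not for these five.

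**Working it through.** The documents give no figure to reproduce here and no reader-agreement data. The metric swap and the vote-pattern counts follow from the SAP's rules alone. The 2×2 tables and reader probabilities are assumptions.

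**(a) Positive class**

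Assumed table: 240 patients, 24 abnormal on the expert exam, 14 of these abnormal on the novice exam, and 6 false alarms.

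- Abnormal positive: TP = 14, FN = 10, FP = 6, TN = 210.
- Normal positive: TP = 210, FN = 6, FP = 10, TN = 14.

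| Metric | Abnormal positive | Normal positive |
|---|---|---|
| Sensitivity TP/(TP+FN) | 14/24 = 58.3% | 210/216 = 97.2% |
| Specificity TN/(TN+FP) | 210/216 = 97.2% | 14/24 = 58.3% |
| Precision TP/(TP+FP) | 14/20 = 70.0% | 210/220 = 95.5% |
| F1 = 2TP/(2TP+FP+FN) | 28/44 = 0.64 | 420/436 = 0.96 |
| Accuracy | 224/240 = 93.3% | 224/240 = 93.3% |

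The swap of sensitivity and specificity is exact for any table. Precision becomes the negative predictive value for abnormality.

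Extreme case: novice exams show none of the 24 and raise no false alarm. With normal as positive, TP = 216, FP = 24 and FN = TN = 0. Sensitivity is 216/216 = 100%, precision 216/240 = 90.0%, F1 432/456 = 0.95 and specificity 0/24 = 0%.

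**(b) Vote before pooling, five readers answering**

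The word 'most' is not defined in 5.4.2.2, so both readings were enumerated: a strict majority (more than half) and a plurality (the single largest group).

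| Endpoint type | Vote patterns | At least 3 abnormal votes | No result, strict majority | No result, plurality | Recorded normal, plurality |
|---|---|---|---|---|---|
| LV/RV size (4 categories) | 56 | 46 | 16 | 12 | 1 |
| Valves (3 categories) | 21 | 15 | 3 | 3 | 0 |

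Every pattern without a result has at least three abnormal votes. Examples:

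- Size, 1 normal, 2 hypertrophy, 2 dilation: four of five readers saw an abnormality, yet there is no result under either rule.
- Size, 2 normal and 1 for each abnormal type: recorded as normal under plurality, dropped under strict majority.
- Valve, 1 normal, 2 structurally abnormal, 2 suspected device: no result under either rule.

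With three readers answering, a 1-1-1 split also gives no result, so four readers answering is not the only route.

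Pattern counts are not probabilities. To turn them into shares, take independent readers, each answering 'abnormal' with probability 0.6 to 0.9. Split the abnormal answers by type from equal thirds to 80/15/5 (size) or from 50/50 to 95/5 (valves). Among exams with at least three abnormal votes, exact multinomial sums give:

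- Size, strict majority: 10.9% to 74.5% dropped.
- Size, plurality: 8.3% to 46.4% tied, and 0.3% to 11.3% recorded as normal.
- Valves, either rule: 1.5% to 52.2% dropped, none recorded as normal.

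The low ends are at probability 0.9 with the most uneven split, the high ends at 0.6 with equal splits.

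**After pooling first.** With binary answers, three or five responders always give a majority. Only a 2-2 tie among four responders remains, which is the case that the SAP anticipates.

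**The case against.** - **The reading is inferred.** In diagnostic metrics 'positive' usually means that the finding is present, and the protocol's questions point that way. So abnormal may be what the sponsor intends. This stands as a point about intent, but it does not settle the text: the SAP's own binary question points the other way, so the class has to be stated.
- **Nothing is hidden.** Sensitivity and specificity are both reported, accuracy does not change, and the confusion matrix allows recalculation. True. The harm is a misleading label, not lost data.
- **The order is not certain.** One could read the conversion as applying to each cardiologist's answer before the vote, and the four-reader remark would fit that. However, the reference and tested values are defined earlier in the section as the voted category.
- **Plurality is the weaker reading.** SAP 5.4.1 and 5.4.2.1 equate majority with at least 3 of 5. That makes the recorded-as-normal case less likely, but under strict majority more exams are dropped.
- **Part is already handled.** Exams without a majority stay in the matrix, and a further analysis is foreseen, though its trigger and content are not specified. The grouping note in 3.4.2.1 would solve ventricular size if applied before the vote, but it is optional, has no stated timing and omits the valves. SAP 5.5.2 reports how many exams have at least 3, 4 or 5 readers agreeing, which shows vote splitting but does not correct the metrics.
- **The shares in (b) rest on assumptions.** They do. At the low ends, 24 majority-abnormal exams would lose about 3 for size (24 × 0.109 = 2.6) and fewer than 1 for a valve (24 × 0.015 = 0.4).

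**Conclusion.** The concern holds and should be fixed. The positive class is undefined, and on the natural reading sensitivity and specificity are exactly exchanged relative to the protocol's questions. Followed as written, the voting order can remove or, under plurality, misclassify ventricular-size and valve exams that most readers called abnormal, but never exams that most called normal. These conclusions need no assumed numbers. How many exams would be lost cannot be known from the documents. The ranges above are wide, and their upper ends need near-even splits between abnormal types and readers close to equipoise. These are secondary endpoints without a success criterion, so the primary success rule in SAP 3.3 is untouched.

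**What to change.** Amend SAP 5.4.2.2 as follows:

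1. Define the positive class as every answer now mapped to no: abnormal, enlarged, hypertrophy, dilation, reduced, present, dilated, suspected device.
2. For the binary metrics, convert each cardiologist's answer to normal or abnormal first, then take the majority of the binary answers. Only 2-2 ties among four answering readers then remain without a majority.
3. For the multi-category values, state whether 'most' means a plurality or more than half of those answering. State when the grouping in 3.4.2.1 applies, and correct the explanation that a majority fails only because four readers answered.
4. Keep the multi-category confusion matrix as a descriptive table.

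The cost is SAP wording and a small programming change, with no new data. Reported sensitivity, precision and F1 will probably look less favourable than with normal as the positive class.
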